Briefly describe study design and anticipated enrollment, i.e., number of subjects to be enrolled by researchers study-wide and by Partners researchers. Provide a brief summary of the eligibility criteria (for example, age range, gender, medical condition). Include any local site restrictions, for example, “Enrollment at Partners will be limited to adults although the sponsor’s protocol is open to both children and adults.”

A total of 200 ED patients will be recruited and randomized for this project.

Inclusion criteria: 1) age \geq 18 years patients and either a parent/guardian of a pediatric/cognitively disabled patient in the MGH ED, 2) triaged to the Acute, CDU, Fast Track, Urgent, and Pediatrics areas, 3) English- or Spanish-speaking, and 4) capable of informed consent. *Exclusion criteria:* 1) patients unwilling to have the interview audio-recorded, 2) medically unstable patients, and 3) Section 12, lack of capacity medical hold (yellow paper), sexual assault, child abuse, and emotionally distressed patients.

Bilingual research assistants (RA) will screen patients for eligibility based on the above predetermined criteria. Potential study participants will be approached by trained RAs who will verbally consent patients for participation in the study. Patients who provide consent will be randomized to oral v. written (iPad) screening for completion of the Partners HealthCare HRSN screening tool. We plan to enroll 100 patients into each of the oral v. iPad screening groups, to examine potential differences in satisfaction and screening responses. A subset of enrolled patients will be invited to participate in an in-depth interview. Participants will be compensated \$20 for the additional time to complete the interview component of the study. We will purposively sample enrolled participants to balance recruitment across 4 groups defined by screening strategy (oral v. iPad) and health literacy (high v. limited). The sampling strategy is purposive, designed to make sure the full range of themes is elicited within each prespecified group. We will enroll in the interview portion of the study until thematic saturation is reached in each of the four groups.

Briefly describe study procedures. Include any local site restrictions, for example, “Subjects enrolled at Partners will not participate in the pharmacokinetic portion of the study.” Describe study endpoints.

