Bilingual research assistants (RA) will screen patients for eligibility based on the predetermined criteria and approach eligible patients with a brief description of the study and opportunity for participation. Interested participants will complete a verbal consent process to reduce the barriers to participation, a brief demographic questionnaire, and an assessment of health literacy (Newest Vital Sign) followed by the Partners Healthcare HRSN screener randomized to an oral v. iPad screening strategy. Randomization will occur after consent. Randomization will be operationalized through use of a randomization list. We will make 500 randomization assignments for an expected study enrollment of 200.

After completion of the screening tool, participants will complete a secondary questionnaire asking about satisfaction with the process, the presence of additional HRSN not recorded by the Partners HealthCare screener, and their perspectives on screening. At the conclusion, all participants will be provided with standardized, bilingual list of community resources to address each of the screening domains. For patients who explicitly request assistance with making these connections, the clinical team will be informed, and a Social Services consult (or ED navigator consult when appropriate) will be recommended.

A subset of enrolled patients will be invited to participate in an in-depth interview. We have chosen to use qualitative interviews to identify the range of opinions regarding screening for HRSN in the ED setting. We will purposively sample to balance recruitment across 4 groups defined by screening strategy (oral v. iPad) and health literacy (high v. limited). The sampling strategy is purposive, designed to make sure the full range of themes is elicited within each prespecified group. Interviews are continued until thematic saturation is reached for each group, the point at which interviews are no longer revealing new information about the primary topic of interest. Although there is no formal sample size for qualitative studies, thematic saturation is generally reached by 12 interviews per group,² and therefore we anticipate completing 48 interviews. As we anticipate fewer Spanish-speaking participants based on ED demographics, all Spanish-speaking patients will be invited to participate in the qualitative interview to ensure a diverse representation of perspectives. These 30-minute qualitative interviews will cover

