domains regarding screening preferences, barriers and facilitators to disclosure of HRSN in the ED, perception of screening practices, and the opportunity to identify HRSN that may have been missed by the Partners HealthCare HRSN screening tool. All interviews will be recorded, encryption-stored, professionally transcribed, and qualitative software will be used for analysis.

¹ Osborn CY, Weiss BD, Davis TC, et al. Measuring adult literacy in health care: performance of the newest vital sign. *Am J Health Behav.* 2007;31(Suppl 1):S36-46.

² Guest G, Bunce A, Johnson L. How many interviews are enough? An experiment with data saturation and variability. *Field Methods.* 2006;18(1):59-82.

For studies involving treatment or diagnosis, provide information about standard of care at Partners (e.g., BWH, MGH) and indicate how the study procedures differ from standard care. Provide information on available alternative treatments, procedures, or methods of diagnosis.

N/A

Describe how risks to subjects are minimized, for example, by using procedures which are consistent with sound research design and which do not unnecessarily expose subjects to risk or by using procedures already being performed on the subject for diagnostic or treatment purposes.

Although it is not anticipated that any of the screening or qualitative interview questions will cause emotional discomfort or distress, participants are informed that they may decline to answer any questions and/or withdraw from the study altogether.

Describe explicitly the methods for ensuring the safety of subjects. Provide objective criteria for removing a subject from the study, for example, objective criteria for worsening disease/lack of improvement and/or unacceptable adverse events. The inclusion of objective drop criteria is especially important in studies designed with placebo control groups.

Should a patient or parent wish to withdraw at any point they can do so. In addition, if the clinical team feels a patient is no longer appropriate to participate in the study (e.g., worsening disease of the patient or child, need for potentially distressing clinical communication), we will stop the interview and use only the portion of the data already collected.

FORESEEABLE RISKS AND DISCOMFORTS

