The risks and benefits of the research must be fairly distributed among the populations that stand to benefit from it. No group of persons, for example, men, women, pregnant women, children, and minorities, should be categorically excluded from the research without a good scientific or ethical reason to do so. Please provide the basis for concluding that the study population is representative of the population that stands to potentially benefit from this research.

No group of persons will be excluded from the research study based on gender, race, ethnicity, or health insurance status. We will enroll only patients ≥ 18 . For patients under age 18, parents/guardians will be approached for consent and participation.

When people who do not speak English are excluded from participation in the research, provide the scientific rationale for doing so. Individuals who do not speak English should not be denied participation in research simply because it is inconvenient to translate the consent form in different languages and to have an interpreter present.

English- and Spanish-speaking patients will be approached for enrollment in this study.

For guidance, refer to the following Partners policy:

Obtaining and Documenting Informed Consent of Subjects who do not Speak English

https://partnershealthcare-public.sharepoint.com/ClinicalResearch/Non-English_Speaking_Subjects.1.10.pdf

RECRUITMENT PROCEDURES

Explain in detail the specific methodology that will be used to recruit subjects. Specifically address how, when, where and by whom subjects will be identified and approached about participation. Include any specific recruitment methods used to enhance recruitment of women and minorities.

Bilingual RA staff will round in the ED to identify potentially eligible patients. Patients will be approached in the ED by a CITI-certified RA and informed about the opportunity to complete a voluntary and anonymous HRSN screener. If the patient expresses interest in learning more, the trained RA will explain the study to the patient, answer all questions, and obtain verbal consent prior to proceeding with the HRSN screening +/- qualitative interview. A screening log with participants names will be kept to avoid duplicate enrollment.

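### Refusing audio-recording bars a patient from the whole randomised trial, although only the optional in-depth interview is described as recorded

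*Protocol*

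**What the plan says.** Research Design and Methods states that 200 patients will be recruited and randomised, then gives one list of inclusion and exclusion criteria. The first exclusion is "patients unwilling to have the interview audio-recorded". Research assistants "will screen patients for eligibility based on the above predetermined criteria", and consent and randomisation follow. The two arms of 100 are compared "to examine potential differences in satisfaction and screening responses".

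The interview is a separate, later component: "A subset of enrolled patients will be invited to participate in an in-depth interview". The study procedures expect saturation at about 12 interviews in each of four groups (arm by health literacy), "and therefore we anticipate completing 48 interviews". They add that "all Spanish-speaking patients will be invited to participate in the qualitative interview". Directly after describing the 30-minute interviews, the text says: "All interviews will be recorded, encryption-stored, professionally transcribed".

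Under Recruitment Procedures, the assistant will "obtain verbal consent prior to proceeding with the HRSN screening +/- qualitative interview", so the interview is optional at consent. Foreseeable Risks and Discomforts and Data and Safety Monitoring mention recordings only as interview recordings, transcribed for qualitative analysis. The latter lists completed screeners separately from interview transcripts.

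**The concern.** A condition that belongs to one optional component has been placed among the entry criteria for the whole trial. If research assistants follow the list, they turn away patients who would accept the social-needs screener in either form and the satisfaction questionnaire, because those patients object to a procedure most participants are not expected to undergo.

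The subject of the trial makes this more than an untidy list. Patient acceptability is in the hypothesis, and the arms are compared on satisfaction and on what patients report. Background and Significance notes that private space is not always available, that patients may feel embarrassed, and that 33-50% of those approached already decline screening. Verbal consent was chosen to lower barriers to joining. Patients who will not be recorded may differ from others on privacy and disclosure, and the results may then not carry over to them. Recruitment also loses otherwise eligible patients.

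**Working it through.** **Scope of the rule.** Four statements have to be read together.

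1. There is one eligibility list. It directly follows the total to be randomised and is applied before consent and randomisation.
2. No sentence limits the recording exclusion to the interview, and none gives a reason for applying it to everyone.
3. Every mention of recording concerns interviews. Nothing says that the oral screener, the iPad screener or the satisfaction questionnaire is recorded.
4. The interview is by invitation and optional at consent.

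It follows that unwillingness to be interviewed does not exclude a patient, but unwillingness to have that interview recorded does.

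Background and Significance describes oral screening as a form of in-person interview, so one might read the exclusion as referring to the oral screener. That does not rescue the wording: no recording of the screener is described, and the iPad arm has no oral screening to record.

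**Share expected to be recorded.** The plan's own figures reproduce: 4 groups × 12 = 48 interviews and 2 arms × 100 = 200 patients. Then 48/200 = 24%, so about 152 of 200 (76%) are not expected to have a recorded procedure. The 48 is neither a cap nor the number invited, since interviewing runs to saturation and all Spanish speakers are invited.

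**Recruitment under the present rule.** The protocol gives no rate of recording refusal, and the 33-50% decline rate concerns screening in general. If a fraction r of otherwise eligible and willing patients refuse recording (assumed), 200/(1 − r) such patients are needed to randomise 200:

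| r (assumed) | Patients needed |
|---|---|
| 5% | 211 |
| 10% | 223 |
| 20% | 250 |
| 30% | 286 |

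**What moving the rule costs the interviews.** With the rule moved, 200(1 − r) enrolled patients can be interviewed, or 100(1 − r) per arm, against a need of 2 × 12 = 24 per arm. The tightest groups are likely to be those with limited literacy. With a the interview uptake and p the limited-literacy share in an arm, reaching 12 requires 100 × p × (1 − r) × a ≥ 12, so p ≥ 12/[100(1 − r)a]. This treats refusal as independent of literacy.

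| r (assumed) | Available (per arm) | Minimum p, a = 1 | Minimum p, a = 0.5 (assumed) |
|---|---|---|---|
| 0% | 200 (100) | 12.0% | 24.0% |
| 10% | 180 (90) | 13.3% | 26.7% |
| 20% | 160 (80) | 15.0% | 30.0% |
| 30% | 140 (70) | 17.1% | 34.3% |

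The r = 0% row corresponds to the present rule, under which everyone randomised is willing to be recorded.

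**The case against.** The strongest reply is that the criterion was always meant for the interview. It names the interview, the interview portion has its own enrolment step, and the form asks only for a brief summary of eligibility. Willingness to be recorded also cannot be known before a patient is approached. This reading is plausible, but the protocol does not state it, staff work from the written list, and the same one-line correction is needed either way.

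A second reply is that a trial-wide rule is a deliberate trade-off. The qualitative work is one of two aims, interviewees are sampled from enrolled patients by arm and literacy, and both are known only after consent. Requiring willingness at entry keeps everyone available for a scarce group. The protocol does not give this reason. The rule would not secure it either, because a patient can be randomised and then decline the interview. The point about scarce groups does stand in part: no literacy distribution is given, so how much more slowly they would fill is not established.

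Third, the harm is not demonstrated. That is correct as far as size goes. That refusers are more privacy-sensitive is a reasonable possibility, not a finding, and some of them might have declined screening anyway.

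**Conclusion.** The concern holds as a matter of text and design. As written, the protocol restricts who is randomised on the strength of a procedure expected in about 24% of participants, perhaps more, and gives no reason. The comparison among enrolled patients is not biased, because the rule precedes randomisation and falls on both arms alike. What is affected is generalisability, along with some avoidable loss of willing patients. Neither can be sized from the protocol; the recruitment and availability figures rest on assumed refusal rates of up to 30% and an assumed uptake of 100% or 50%. It is worth correcting because the correction is cheap. Confidence is medium, since the sponsor may have intended an interview-only rule.

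**What to change.** Delete the recording exclusion from the trial-level criteria and state it as a condition for the in-depth interview only, asked when that interview is offered; for example: *interview component: not eligible if unwilling to be audio-recorded*. If the sponsor does intend it to apply to all 200, the protocol should say so and give the reason.

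The change is a one-line amendment. The planned 200 patients, the two arms and the anticipated 48 interviews stay as they are. The downside is that some enrolled patients will not be available for interview, so the limited-literacy groups and the Spanish-speaking interviewees may take longer to fill; progress in these groups should be watched during recruitment.

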The Partners HealthCare HRSN screening tool is currently in use in the MGH ED to screen Medicare and Medicaid beneficiaries for unmet HRSN related to 9 major categories: transportation, food, housing, ability to pay utility bills, ability to pay for medicines, employment, education, childcare, and elder care. In its current form, HRSN screening is carried out as a one-on-one interview that can last up to an hour, conducted by the ED Medicaid navigator, with patients who present during weekday/daytime hours. Not all patients approached agree to the screening however (33-50% of patients approached for screening decline to participate), and patients have reported unmet needs outside of the 9 major categories screened.

Screening in the ED is exceptionally challenging. Patients may feel too ill to divert their attention from their state of health and must be readily available for the multiple interruptions for reassessments and diagnostic testing. Additionally, private spaces are not always available, and patients may feel embarrassed, or simply too exhausted, to discuss their needs. The most effective screening method for HRSN under these challenging conditions—in other words, the most acceptable to patients, the most efficient in identifying salient, pressing, and actionable barriers to health, and the least disruptive to the flow of emergency care—has not yet been identified. Finally, the impact of HRSN screening is greatest when coupled with streamlined linkages and referrals to community-based social services capable of acting upon the information obtained and assisting individuals to meet their health-related social needs.

The overarching goal of this project is to optimize HRSN screening in the ED. Screening in the health care setting can be achieved via oral (in-person interviews) or written (computer-based surveys) modalities. Using the established Partners HealthCare HRSN screener (permission for use granted), we will examine patients' satisfaction with the screening process

using both modalities. Additionally, we will evaluate HRSN identified and missed by the established screener to understand whether additional or alternative screening questions are relevant and needed for the ED patient population. Finally, we will provide participants with linkages and referrals to community organizations based on their identified unmet HRSN.

RESEARCH DESIGN AND METHODS

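### Does the protocol's silence on who holds the randomization list leave the oral versus iPad comparison open to selection bias?

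*Protocol*

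**What the plan says.** Under Research Design and Methods, the study-procedures text gives the timing, "Randomization will occur after consent", and the mechanism, "Randomization will be operationalized through use of a randomization list. We will make 500 randomization assignments for an expected study enrollment of 200". No section names a person who generates or holds the list, or describes how an assignment is released.

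The same section says who recruits: "Bilingual research assistants (RA) will screen patients for eligibility based on the predetermined criteria and approach eligible patients". The exclusions include "medically unstable patients" and a group ending in "sexual assault, child abuse, and emotionally distressed patients", so some of them call for judgment. Under Recruitment Procedures, "the trained RA will explain the study to the patient, answer all questions, and obtain verbal consent prior to proceeding with the HRSN screening". The plan is for 100 patients per group, "to examine potential differences in satisfaction and screening responses".

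The study-procedures text also lists the steps in order: consent, a demographic questionnaire, the Newest Vital Sign literacy assessment, then the screener in the randomized form.

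**The concern.** A list made in advance protects a trial only if the person deciding whom to approach cannot see the next line. Randomizing after consent fixes the order of formal steps. It does not stop someone with the list in hand from choosing or excluding patients with the next arm in mind.

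Three features make this matter here. One group of staff identifies patients, applies judgment-based exclusions and takes consent. Oral and iPad screening cannot be masked. Satisfaction, one of the two outcomes named for the comparison, is the patient's own rating. Background and Significance also suggests a motive: "In its current form, HRSN screening is carried out as a one-on-one interview that can last up to an hour", in a department where privacy is scarce and patients may be worn out.

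The direction of any bias is unknown. Passing over exhausted patients when oral is next would favor oral; passing over patients who seem to read poorly when iPad is next would favor iPad. Selection of this kind cannot be undone once enrollment has ended.

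**Working it through.** **What the text settles and what it leaves open**

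- Timing of assignment: settled (after consent).
- Source of assignment: settled (a list with more lines than expected patients).
- Custody and release: not stated. The locked-cabinet text under Foreseeable Risks, Data and Safety Monitoring, and Privacy and Confidentiality protects participants' information and does not mention the list. Consent Procedures separates the consenting staff from the clinical team, not from the list. REDCap is named only for demographic information.

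Nothing here conflicts with concealment. Numbered opaque envelopes, or release by someone outside recruitment, would satisfy every sentence. The plan does not prescribe open access.

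**How large the bias could be if the list were visible**

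Inputs from the protocol: 100 patients per arm. Assumptions not in the protocol: a share p = 0.30 of eligible patients rates satisfaction d SD lower; a recruiter passes over a fraction s of them in one arm only, and a fraction e of all other patients by mistake; a two-sided 5% z-test with unit SD. The protocol states no test or significance level.

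- Share retained: k = p(1 − s) + (1 − p)(1 − e)
- Low raters among those retained: q = p(1 − s)/k
- Bias = d(p − q)
- Patients passed over per 100 enrolled = 100(1 − k)/k
- SE = √(2/100) = 0.1414 SD
- False-positive rate = P(|Z + bias/SE| > 1.96)

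Example, d = 0.5, s = 0.5, e = 0: k = 0.15 + 0.70 = 0.85; q = 0.15/0.85 = 0.176; bias = 0.5 × (0.30 − 0.176) = 0.062 SD; passed over = 100 × 0.15/0.85 = 17.6; bias/SE = 0.437; false-positive rate 7.2%.

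| d | s | e | Passed over | Bias (SD) | False-positive rate |
|---|---|---|---|---|---|
| 0.5 | 0.25 | 0 | 8 | 0.028 | 5.5% |
| 0.5 | 0.5 | 0 | 18 | 0.062 | 7.2% |
| 0.5 | 0.5 | 0.15 | 34 | 0.049 | 6.4% |
| 0.5 | 0.5 | 0.25 | 48 | 0.039 | 5.9% |
| 0.5 | 1 | 0 | 43 | 0.150 | 18.5% |
| 0.3 | 1 | 0 | 43 | 0.090 | 9.8% |
| 0.8 | 1 | 0 | 43 | 0.240 | 39.6% |

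The large rates need every low rater to be recognized and excluded from one arm. With partial steering and some errors of recognition, the bias at d = 0.5 is 0.04 to 0.05 SD, against a 95% half-width of 1.96 × 0.1414 = 0.277 SD.

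**Two figures that do not measure the risk**

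- Background and Significance reports that 33–50% of patients decline. Carried over, 200/0.67 = 299 to 200/0.50 = 400 patients would be approached, and 99 to 200 would not enroll. Those are patients' own refusals of the navigator's interview, not recruiters' choices.
- The list has 500 − 200 = 300 spare lines. The calculation above passes over patients, not lines, and nothing in the protocol permits skipping a line.

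**The case for a change.** The strongest case for a change is that concealment is part of running the trial, must work before the first patient, and cannot be supplied by an analysis plan. The protocol chose to describe its randomization and stopped short of the part that protects it. A sentence would cost almost nothing, and if the list were left open to recruiters no later analysis could repair the damage. The Co-PIs review completed screeners and interview transcripts, which would not reveal patients who were never approached.

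Much of that stands. The text is silent, and the sequence of consent before randomization does not by itself hide the next line.

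Two parts are weaker than they look. First, the records are not as blind as suggested. Privacy and Confidentiality says names are logged to avoid approaching the same person twice, so the log plausibly covers people approached who then decline. Literacy and demographics are collected from participants, so steering by apparent reading ability could show as an imbalance between arms. Steering by exhaustion could not be seen this way. Second, the argument shows that a bad execution is possible, not that the plan calls for one. The form asks for a brief description, and custody of a list is the sort of detail a working procedure usually holds.

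**Conclusion.** The concern does not call for a change. The protocol leaves custody and release of the list unwritten, but states nothing wrong about them, and routine concealed release fits the text exactly. This is a gap that study staff ordinarily fill sensibly; following the plan as written does not by itself bias the comparison.

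If the list were in fact visible to recruiters, light or imperfect steering would move a nominal 5% error rate to roughly 5.5–7.2% at d = 0.5. Rates of 9.8–39.6% across d = 0.3 to 0.8 arise only if every low rater is identified and passed over in one arm. All of these rest on assumed values for the share of low raters, their difference in satisfaction, and the recruiter's behavior; none comes from the protocol.

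The conclusion assumes that staff release assignments in order without showing the next line to whoever is recruiting. The document gives no reason to think otherwise, though it cannot confirm it.

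### Does a 500-entry randomisation list for 200 patients undermine the planned 100 per arm and the literacy and language groups?

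*Protocol*

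**What the plan says.** All the relevant text is in the Protocol under Research Design and Methods.

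- **Size.** The enrolment paragraph says "A total of 200 ED patients will be recruited and randomized for this project" and "We plan to enroll 100 patients into each of the oral v. iPad screening groups".
- **Allocation.** The study-procedures text says "Randomization will occur after consent", then "Randomization will be operationalized through use of a randomization list", then "We will make 500 randomization assignments for an expected study enrollment of 200".
- **Order of steps.** After consent and a short demographic form comes "an assessment of health literacy (Newest Vital Sign) followed by the Partners Healthcare HRSN screener randomized to an oral v. iPad screening strategy".
- **Four groups.** For the interview subset, "We will purposively sample to balance recruitment across 4 groups defined by screening strategy (oral v. iPad) and health literacy (high v. limited"). About 12 interviews per group, 48 in all, are expected.
- **Language.** Fewer Spanish speakers are expected, with no number given, and all of them are invited to the interview.

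The protocol does not say whether the list is blocked or stratified, who holds it, or how the next entry is revealed. It also rules none of these out.

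**The concern.** Only 200 of the 500 entries are expected to be used. If the list is balanced only at its end, or not at all, the arms will rarely stand at exactly 100 each when enrolment closes.

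The protocol also names groups defined by arm and health literacy and expects few Spanish speakers, yet mentions neither factor in connection with allocation. Both could affect how an oral or iPad screener is received, so uneven small subgroups could blur the comparison of satisfaction and responses.

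Randomisation is fixed in time only as following consent. On a loose reading, the arm could be known before the literacy test is scored. If research assistants could read ahead on the list, they could foresee the next arm in a study that cannot be masked and has a subjective outcome.

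**Working it through.** **Inputs.** From Research Design and Methods: 200 randomised, 100 per arm (so 1:1), list length 500, 12 interviews per group. From Background and Significance: 33-50% of patients approached for the existing screening decline. Assumed, because the protocol gives no figure: effect 0.4 SD, two-sided alpha 0.05, and all subgroup sizes and shares.

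**1. The plan's own figure.** 100 + 100 = 200, which agrees. The protocol gives no alpha, power or effect size, so 100 per arm cannot be rebuilt from a power formula.

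**2. Split after 200 patients, by type of list.**

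| List | SD of one arm's size | P(exactly 100:100) | 95% range | P(90:110 or worse) |
|---|---|---|---|---|
| Unblocked, Binomial(200, 0.5) | √(200 × 0.25) = 7.07 | 5.6% | 86-114 | 17.9% |
| Balanced only over 500, Hypergeometric(500, 250, 200) | √(200 × 0.25 × 300/499) = 5.48 | 7.3% | 89-111 | 8.3% |
| Blocks of 2, 4, 8, 10 or 20 | 0, since 200 is a multiple of the block size | 100% | 100-100 | 0% |

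With blocks of 6, 200 = 33 × 6 + 2, so the split is 100:100 or 99:101. The low probabilities describe two list types that the protocol does not specify. List length alone does not cause them.

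**3. Cost of an uneven split.** Relative efficiency is 4·n₁·n₂/N². Power is Φ(0.4/√(1/n₁ + 1/n₂) − 1.96).

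| Split | Efficiency | Power at 0.4 SD |
|---|---|---|
| 100:100 | 1.000 | 80.7% |
| 90:110 | 4 × 90 × 110/40,000 = 0.990 | 80.4% |
| 86:114 | 4 × 86 × 114/40,000 = 0.980 | 80.0% |

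At the edge of the 95% range for the least favourable list, the loss is 0.7 of a power point.

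**4. Small subgroups (sizes assumed, unblocked list).** The probability of a 60:40 split or worse is 50% for 20 patients, 27% for 40 and 16% for 60. A 12:8 split still keeps 4 × 12 × 8/20² = 96% efficiency within that subgroup. The design text announces no arm comparison within language or literacy subgroups.

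**5. Interview cells.** Each literacy level needs about 12 interviewees per arm. The probability that one arm has fewer than 12 patients at a given level is 20% if that level has 30 patients, 0.6% if 40, and below 0.0001% if 60.

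**6. Spare entries.** The decline rate implies 200/0.67 = 299 to 200/0.50 = 400 approaches, which does not explain 500. It need not. The rate belongs to the existing navigator interview, and patients who decline are never randomised because allocation follows consent. In a simple or blocked list, the unused entries have no effect on the first 200.

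**7. Would stratified blocks secure 100 per arm?** Simulation with four literacy-by-language strata (assumed shares 45/35/10/10% or 60/25/5/10%) gives exactly 100:100 in about 43% of trials with blocks of 4 and about 37% with blocks of 6. The 95th percentile of the arm difference is 4 patients. Plain unstratified blocking meets the 100:100 target better, so stratification is a preference.

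**8. Timing.** The literacy test is listed ahead of the randomised screener. Allocation after consent is compatible with revealing the arm once that test is done.

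**The case for a change.** The best argument on the other side is that sequence structure, concealment and timing of reveal are matters of trial conduct. They are not analysis, and they cannot be repaired once enrolment starts. Here research assistants find, approach and consent the patients, the arms are open and satisfaction is subjective, so concealment matters. The text would also permit revealing the arm before the literacy test.

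Purposive sampling can draw only on patients already allocated to each arm. With 30 limited-literacy patients there is a 20% chance that one arm has fewer than 12. If refusals meant that 16 per arm were needed, the chance of falling short would be about 15% with 40 such patients (both numbers assumed). Nor does purposive sampling help the quantitative comparison.

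Part of this stands. The wording does not guarantee 100:100, and a sentence on blocks and on revealing the arm after the literacy test would be useful. But an absent detail is not a wrong statement. No text says that the research assistant holds the list or reads it in order. Block sizes are often kept out of protocols on purpose, and the details may be in a plan that is not shown. The subgroup probabilities depend on assumed sizes and describe chance imbalance. Standard errors allow for such imbalance, and covariate adjustment could reduce it, since literacy and demographics are collected from every participant.

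**Conclusion.** The concern does not hold. The protocol commits to a list with spare entries, used after consent. Nothing in that contradicts 100 per arm, and a list in small blocks delivers it exactly. Under the least favourable reading, an unblocked list, randomisation still gives a valid comparison, and the loss at 86:114 is 2% of efficiency, or 0.7 of a power point.

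The literacy groups belong to the interview sampling and are balanced by that sampling. Language-by-arm groups do not exist in the protocol, and the literacy test is already listed ahead of the randomised screener.

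This conclusion assumes 1:1 allocation, and the power figures also assume a 0.4 SD effect and two-sided alpha of 0.05. The subgroup figures depend on sizes that the protocol does not give. Stating the block structure and the moment of reveal would be a courtesy to the reader; leaving them out is no error in the design.
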